8.2.3 Missing Doses

All efforts should be made to administer IP on all of the scheduled days of each 28-day treatment cycle. Any missed doses during that period should not be taken after the last scheduled day of administration, but should be returned by the subject for IP accountability.

8.2.4 Dose Modifications

All subjects in Cycle 1 or 2 will receive CC-486 for 14 days of a 28-day cycle schedule. Subjects may increase to a 21-day schedule (Level +1) at the conclusion of Cycle 2 if no Grade 3 or 4 toxicities requiring dose delay or reductions and if no evidence of hematological improvement upon discussion and agreement between the investigator and the Medical Monitor.

When the dose level is adjusted, weekly hematology monitoring is required for 2 cycles including the cycle in which the adjusted dose or dosing schedule was applied as well as the following cycle, see Section 8.2.5 Re-treatment Criteria.

The dose/treatment schedule modifications steps for 14 days schedule are:

	Dose/schedule		
	300 mg/21d		Level +1
Dose escalation step	300 mg/14d		Level 1
Dose escalation step	200 mg/14d	Dose reduction step	Level -1
Dose escalation step	200 mg/7d	Dose reduction step	Level-2

All efforts should be made to dose IP according to schedule without cycle delay, dose interruption and reduction. Subjects will be monitored for hematologic toxicity and non-hematologic toxicity with the National Cancer Institute (NCI) Common Terminology Criteria for Adverse Events (CTCAE, Version 4.0) used as a guide for the grading of severity.

If a certain level of toxicity is observed (eg, [Table 2](#)) and considered by the investigator to be at least possibly related to treatment, IP dosing may be interrupted, delayed or modified. The investigator may contact the Medical Monitor prior to any treatment adjustment. Please note that in the event neutropenia Grade 4 is observed, or any adverse event that would put a subject at unacceptable risk in the investigator’s opinion, IP dosing may be interrupted, delayed or modified even if not considered by the investigator to be at least possibly related to treatment.

A maximum of one dose reduction step to 200 mg is permitted in the event of toxicity. A maximum of two treatment schedule modifications, stepwise first from 21 to 14 days and then from 14 days to 7 days, at a dose of 200 mg once a day are permitted in the event of continuing toxicity. Subjects are not allowed to receive less than 200 mg IP or be scheduled to receive treatment for less than 7 days.

Subjects who have their IP dose reduced or treatment schedule modified may return to their original dose and/or schedule in a step-wise fashion upon discussion and agreement between the investigator and the Medical Monitor provided that the increased dose or treatment schedule is tolerable and at least two additional treatment cycles have occurred since the dose reduction or treatment schedule modification. The treatment schedule should first be increased from 7 to 14 days and then 14 to 21 days, followed by a dose escalation step from 200 to 300 mg.

The dose/treatment schedule modifications steps for 21 days schedule are:

	Dose/schedule		
	300 mg/21d		Level 1
Dose escalation step	200 mg/21d	Dose reduction step	Level -1
Dose escalation step	200 mg/14d	Dose reduction step	Level -2
Dose escalation step	200 mg/7d	Dose reduction step	Level -3

Refer to [Section 8.2.5](#) if, despite the temporary interruption, delay or modification of study treatment, the toxicity persists for more than 42 days and is considered by the investigator to be at least possibly related to study treatment.

Following any modification of study treatment or if a dose is missed, the subject should stay on the visit schedule as specified in [Table 1](#). Unscheduled visits may occur to monitor the subject’s toxicities if necessary.

Dose Modification for Febrile Neutropenia

Any subject who experiences febrile neutropenia \geq Grade 3 will have IP held until fever has resolved; must be afebrile for 3 days before re-starting IP, see [Table 2](#). Administration of antibiotic, antiviral and antifungal therapy is strongly recommended.

Dose Modification for Neutropenia Grade 4

- Grade 4 ANC at Day 1 of a cycle:

Subjects with Grade 4 ANC at Day 1 of a cycle are going to be dosed for a maximum of 14 days on the respective dose level 300 mg or 200 mg or a maximum of 7 days when already on a 14-day dosing schedule. If a subject is stable or improving over several cycles, a discussion with the Medical Monitor is necessary to determine the dose schedule, see [Table 2](#).

- ANC change during a cycle:

Subjects who experience a drop in the ANC during a cycle (e.g. from Grade 3 to Grade 4 or for $> 50\%$ drop for subject with Grade 4 at Day 15 or Day 8 [Day 8 during the 1st two cycles]) will hold the dose for the remaining cycle. If subject is stable or improving for several cycles, a discussion with the Medical Monitor is necessary to determine the dose schedule, see [Table 2](#).

- If dose was held, the start of next cycle is based on ANC recovery, see flow chart in [Section 8.2.5 Re-Treatment Criteria](#), and see dosing table above.

Dose Modification for Diarrhea

It is recommended that subjects experiencing diarrhea be managed according to the guidelines provided in [Appendix H](#). Anti-diarrhea medication may be administered as prophylaxis against diarrhea and for treatment of any adverse events of diarrhea. Dose modifications for diarrhea (\geq Grade 3) are summarized in [Table 2](#).

Dose Modification for Nausea and Vomiting

A serotonin (5-HT₃) receptor antagonist (eg, ondansetron) (or other comparable medication) may be administered as an antiemetic approximately 30 minutes prior to IP administration at the investigator's discretion. Antiemetic medication(s) may be administered for treatment of any adverse events of nausea and/or vomiting. Dose modifications for nausea and vomiting (\geq Grade 3) are summarized in [Table 2](#).

Dose Modification for Renal Dysfunction and Abnormal Serum Electrolytes

If unexplained elevations of serum creatinine or electrolyte disturbances occur, dose or schedule modifications may be implemented as summarized in [Table 2](#).

Dose Modification for Weight Change

No dose adjustment should be made for weight loss or gain alone; however, the reason for weight loss (eg, significant nausea, vomiting, anorexia, etc.) or weight gain (eg, peripheral edema) should be investigated and may require a dose modification as specified in [Table 2](#).

Dose Modification for Other Treatment-Related Non-hematologic Toxicity

Any subject who experiences a treatment-related non-hematologic toxicity \geq Grade 3, that is an escalation from baseline status (see [Section 10.4](#) for baseline definition), may have IP dosing temporarily interrupted until the toxicity returns to \leq Grade 2. Dose modifications for \geq Grade 3 non-hematologic toxicity are summarized in [Table 2](#).

Dose modification for hematologic or non-hematologic adverse events that would put a subject at unacceptable risk in the investigator's opinion (independent of IP relationship)

Any subject who experiences any hematologic or non-hematologic adverse event \geq Grade 2, that is an escalation from baseline status (see [Section 10.4](#) for baseline definition) and would put a subject at unacceptable risk in the investigator's opinion, may have IP dosing temporarily interrupted until the adverse event returns to \leq Grade 1. Dose modifications for \geq Grade 2 hematologic or non-hematologic adverse events, that would put a subject at unacceptable risk in the investigator's opinion (independent of IP relationship), are summarized in [Table 2](#).

Table 2: Guidelines for Dose Modifications

NCI CTCAE Toxicity Grade	Action

Febrile Neutropenia (≥ Grade 3)
	
 • Hold IP until fever has resolved. • Antibiotic, antiviral and antifungal therapy is strongly recommended. • Resume IP at next lower dose level (see dosing table above) after the fever has resolved and ANC recovery. Contact Medical Monitor. Must be afebrile for 3 days before re-starting IP. • Secondary prophylaxis with G-CSF is strongly recommended.

Neutropenia Grade 4 (related or unrelated to IP)
	
Pre-existing Neutropenia Grade 4
 
 • Subjects with G4 ANC at D1 of a cycle are going to be dosed for a maximum of 14 days on the respective dose level 300 mg or 200 mg or a maximum of 7 days when already on a 14-day dosing schedule. 
If subjects are stable or improving for several cycles, a discussion with the Medical Monitor is necessary to determine the dose schedule.
 
 • If dose was held, the start of next cycle is based on ANC recovery, see flow chart in Section 8.2.5 Re-Treatment Criteria • If the subject continues to experience neutropenia Grade 4 during 2 consecutive cycles, the treatment schedule may be reduced one step. Secondary prophylaxis with G-CSF is strongly recommended. 
Subjects experiencing worsening of Neutropenia to Grade 4 under IP treatment
 
 • Subjects that experience a drop in the ANC during a cycle (e.g., from G3 to G4 or for > 50% drop for subject with G4 at Day 15 or Day 8 [Day 8 during the 1st two cycles]) will hold the dose for the remaining cycle. 
If subject is stable or improving for several cycles, a discussion with the Medical Monitor is necessary to determine the dose schedule.
 
 • If dose was held, the start of next cycle is based on ANC recovery, see flow chart in Section 8.2.5 Re-Treatment Criteria.
	
 • If the subject continues to experience neutropenia Grade 4 during 2 consecutive cycles, the treatment may be reduced one step. Secondary prophylaxis with G-CSF is strongly recommended.

Table 2: Guidelines for Dose Modifications

NCI CTCAE Toxicity Grade	Action
Diarrhea (≥ Grade 3)	
 • Interrupt IP and provide adequate/maximum medical intervention • Resume IP at same dose when toxicity resolves to ≤ Grade 1 • If event reoccurs upon re-challenge or during next treatment cycle, reduce IP dose to 200 mg. • If event reoccurs at same intensity once IP dose is reduced to 200 mg, follow the steps above and modify the treatment schedule at a dose of 200 mg once a day.
Nausea and/or Vomiting (≥ Grade 3)	
 • Interrupt IP and provide adequate/maximal medical intervention • Resume IP at same dose when toxicity resolves to ≤ Grade 1 • If event reoccurs upon re-challenge or at same intensity during next treatment cycle, reduce dose to 200 mg • If event reoccurs at same intensity once IP dose is reduced to 200 mg, follow the steps above and modify the treatment schedule at a dose of 200 mg once a day.
Renal Dysfunction	
 • For unexplained elevations of serum creatinine, delay the start of the next cycle of treatment until values return to baseline. Reduce IP dose in the next cycle of treatment to 200 mg. • The treatment schedule at a dose of 200 mg once a day can be modified if the elevation of serum creatinine recurs in the subsequent cycle. • Discontinue IP if similar unexplained renal and/or electrolyte disturbances subsequently persist or recur during the next cycle of treatment.
Other ≥ Grade 3 non-hematologic treatment-related toxicities	
 • Interrupt IP dosing and provide medical intervention as appropriate • Resume IP at same dose when toxicity resolves to ≤ Grade 2 • If event reoccurs upon re-challenge or at same intensity during next treatment cycle, IP dose may be reduced to 200 mg once a day • If event reoccurs at same intensity once IP dose is reduced to 200 mg once a day, follow the steps above and modify the treatment schedule at a dose of 200 mg once a day.
≥ Grade 2 hematologic or non-hematologic AEs putting a subject at unacceptable risk in the investigator’s opinion	
 • Interrupt IP dosing and provide medical intervention as appropriate • Resume IP at same dose when toxicity resolves to ≤ Grade 1

Table 2: Guidelines for Dose Modifications

NCI CTCAE Toxicity Grade	Action
(related or unrelated to IP)	
 • If event reoccurs upon re-challenge or at same intensity during next treatment cycle, IP dose may be reduced to 200 mg once a day • If event reoccurs at same intensity once IP dose is reduced to 200 mg, follow the steps above and consider modifying the treatment schedule at a dose of 200 mg once a day.

Key: AE=Adverse Event; ANC=Absolute Neutrophil Count; D=Day; G=Grade; IP=Investigational Product; NCI=National Cancer Institute; CTCAE=Common Terminology Criteria for Adverse Events.

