1.4.1 Risk Assessment

Potential Risk of Clinical Significance	Summary of Data/Rationale for Risk	Mitigation Strategy
Study Intervention - Azacitidine		
Neutropenia and severe infections	In subjects randomized to oral azacitidine 300 mg at 21-day treatment schedule, the most frequent hematological AEs were neutropenia, febrile neutropenia,	To mitigate risk of severe infections, during Cycles 1 and 2 (higher risk period for severe infections) the subjects will receive oral azacitidine for 14 days of a 28-day cycle

Potential Risk of Clinical Significance	Summary of Data/Rationale for Risk	Mitigation Strategy
	
and associated infections. There was an imbalance in incidence of death between the drug and placebo treatment groups. Most of the death cases in the oral azacitidine-treated subjects occurred during the first 56 days on treatment with infections being the leading cause of death. Affected subjects showed lower median ANC at baseline, which could have made them more susceptible for severe infections.
	
schedule. The treatment can be extended to a 21-day schedule after Cycle 2, if a subject did not experience Grade 3 or 4 toxicities requiring dose delay or reductions and if there is no evidence of hematological improvement on 14-day dosing schedule.
 
During the first 2 cycles on treatment subjects' blood counts will be monitored on weekly basis, reducing to biweekly monitoring up to Cycle 12.
 
Guidance for IP dose modification due to toxicities including neutropenia and febrile neutropenia is provided in Section 8.2.4 and Table 2 of the Protocol.
 
A strong recommendation regarding administration of prophylactic fluoroquinolone antibiotics or other recognized prophylactic antibiotics was provided for subjects who develop Grade 4 neutropenia (see Section 9.1).

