8.2.5 Re-treatment Criteria

In order to proceed to the next cycle, subjects must continue to meet entry criteria regarding renal and hepatic function (see Section 7.3). Thus, subjects will have laboratory assessments performed to evaluate organ function prior to starting each cycle (including Cycle 1). Because of the time it takes to obtain results from the central laboratory, samples should be collected early enough prior to starting the next cycle in order to allow sufficient time for review. In the event that immediate laboratory assessment is needed, local laboratory measurement is acceptable for starting the next cycle pending the outcome of the central laboratory assessment (ie, in addition to collecting the local laboratory sample, a second sample should be collected and sent to the central laboratory).

The start of the next cycle will be delayed if the subject does not meet entry criteria regarding renal and hepatic function. If there is a delay of more than 42 days (6 weeks) in the start of the next cycle, the Medical Monitor must be consulted. Study treatment should be discontinued if there is a delay of more than 56 days (8 weeks) in the start of the next cycle, unless, in the opinion of the investigator and the Medical Monitor, the subject is experiencing clinical benefit. Justification of the subject continuing in the study must be recorded in the source documents.

[figure not shown]
For subjects that experience hematotoxicity (ANC or platelet drop to Grade 4, or 50% drop within Grade 4) hematologic recovery is required before starting the next cycle at Day 28. When this occurs later than Cycle 6, contact the Celgene Medical Monitor to discuss if the re-treatment criteria are met.

Hematologic recovery defined as:

ANC or platelets Day 1 \geq ANC or platelets nadir from previous Cycle + (0.5 x [ANC or platelets Day 1 – ANC or platelets nadir from previous Cycle])

Note: Following dose adjustments, cycle duration should return to 28 days.

Figure 2: Decision Tree for Hematologic Recovery

ANC=Absolute Neutrophil Count; IP=Investigational Product.

When the dose level is adjusted, weekly hematology monitoring is required for 2 cycles including the cycle in which the adjusted dose or dosing schedule was applied as well as the following cycle. During those 2 cycles, the following dose modification rule, based on ANC or platelets, is applied:

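### The trigger for requiring hematologic recovery before the next cycle differs between Section 8.2.5 and Section 8.2.4/Table 2, and the printed recovery formula is met by any value at or above nadir

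*Protocol*

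**What the plan says.** Four places in the protocol bear on a subject with Grade 4 neutropenia when a cycle is due.

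- **Section 8.2.4, Grade 4 ANC at Day 1.** "Subjects with Grade 4 ANC at Day 1 of a cycle are going to be dosed for a maximum of 14 days", or at most 7 days when already on a 14-day schedule. The text applies to any cycle and does not say how the subject came to be Grade 4.
- **Section 8.2.4, ANC change during a cycle.** A subject whose ANC drops to Grade 4, or by more than 50% within Grade 4, "will hold the dose for the remaining cycle". Then: "If dose was held, the start of next cycle is based on ANC recovery", with a pointer to the flow chart in 8.2.5.
- **Table 2.** The Day 1 rule reappears under the label "Pre-existing Neutropenia Grade 4", and the within-cycle drop under a separate label for worsening on treatment. Both parts repeat the held-dose condition.
- **Section 8.2.5.** After an ANC or platelet drop to Grade 4, or a 50% drop within Grade 4, "hematologic recovery is required before starting the next cycle at Day 28". No held dose is needed to trigger this. Recovery is defined against the previous cycle's nadir. The closing bullet of 8.2.5, written for the two cycles of closer monitoring after a dose adjustment, goes back to the held-dose condition.

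**The concern.** The same requirement has two triggers. In the main text of 8.2.5 it follows from the blood count. In 8.2.4, in Table 2 and at the end of 8.2.5 it follows from a dose having been held. A subject can meet the first and not the second, and the text does not say which governs. A site working from 8.2.4 and Table 2 alone could start a cycle that a site working from 8.2.5 would delay.

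This concerns the toxicity that Section 1.4.1 lists first among the risks, and that entry cites 8.2.4 and Table 2 as mitigation. Different readings would also enter the exposure summaries in SAP Sections 9.4, 9.5 and 9.8 (cycle length, days dosed per cycle, dose intensity) as site variation rather than toxicity. The rules are still in use: Appendix J applies Section 8.2 dosing and the 8.2.4 modifications in the Extension Phase.

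**Working it through.** No sample size, power or alpha figure is involved. The check covers scheduled days and the printed inequality.

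**1. Can the held-dose condition arise?** Inputs: 14 dosing days in Cycles 1 and 2 (Section 8.2); counts on Days 1, 8, 15 and 22 of those cycles and on Days 1 and 15 of Cycles 3 to 12 (Section 6.6.5); visit windows of ±3 days in Cycles 1 and 2 and ±7 days afterwards (Section 6); no make-up doses after the last scheduled day (Section 8.2.3).

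- Dosing ends on Day 14, so nominal Day 15 and Day 22 both fall after the last dose.
- With the window in Cycles 1 and 2, the Day 15 count can fall on Days 12 to 18, so it may still precede the last dose. The Day 22 count falls on Days 19 to 25 and never does.
- For a subject still on 14 days in Cycles 3 to 12, nominal Day 15 is again after the last dose, but its window runs from Day 8 to Day 22.

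A drop first seen on Day 15 therefore usually leaves nothing to hold, and one first seen on Day 22 of Cycle 1 or 2 always leaves nothing. 8.2.4 names Day 15 as a time at which to hold, which on a 14-day schedule can be done only if the visit is early.

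**2. What does the recovery formula require?** Let D be the Day 1 value, N the previous nadir and P the previous cycle's Day 1 value (ANC, ×10⁹/L).

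- As printed, with the same Day 1 on both sides: D ≥ N + 0.5 × (D − N). This gives 0.5 × (D − N) ≥ 0, so D ≥ N. Any value at or above nadir counts as recovered.
- If the right-hand Day 1 is the previous cycle's: D ≥ N + 0.5 × (P − N) = 0.5 × (P + N).

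**3. When do the two rules diverge?** Grade 4 is taken as ANC below 0.5, from Sections 1.4.1 and 9.1 read together. The ANC values are illustrative.

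| P | N | D | Threshold as printed | Threshold with previous Day 1 | Result at D |
|---|---|---|---|---|---|
| 0.6 | 0.1 | 0.4 | 0.25, met | 0.35, met | Grade 4 but recovered on both readings; the rules are compatible |
| 0.9 | 0.2 | 0.3 | 0.25, met | 0.55, not met | Compatible as printed; on the second reading 8.2.5 delays and 8.2.4 alone doses |

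On the second reading a Grade 4 value can count as recovered only if 0.5 × (P + N) < 0.5, that is P + N < 1.0. As printed, 8.2.5 delays only a subject whose Day 1 value is below the recorded nadir.

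**The case against.** The strongest reply is that the two rules run in sequence. The Study Treatments part of the Protocol Summary, footnote a of Table 1 and Section 8.3 all make further cycles depend on meeting the re-treatment criteria, and footnote a lets Day 1 itself be delayed for recovery. On that reading 8.2.5 decides whether a cycle starts, and the Day 1 rule in 8.2.4 caps its length once it does. 8.2.4 also allows dosing to be interrupted, delayed or modified for any Grade 4 neutropenia, so it does not compel dosing. Table 2 separates pre-existing from worsening neutropenia. After Cycle 6, 8.2.5 refers the question to the Medical Monitor. Figure 2, the decision tree, may settle the matter, but its content is not in the available text.

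Most of this stands, and the sequential reading is the more natural one. It is still an inference: 8.2.4 and Table 2 send only held-dose subjects to 8.2.5. The Table 2 label is missing from the 8.2.4 text, and a subject who dropped last cycle and is still Grade 4 fits the wording of both Table 2 rows. If the formula is taken literally, the divergence largely disappears, but so does nearly all the effect of a requirement stated as mandatory.

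A reader might infer that every subject with Grade 4 ANC on Day 1 receives opposite instructions. The documents do not support that, because recovery is measured from nadir and a subject can be recovered and still Grade 4.

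A reader might also connect the wording with the early deaths, since "Most of the death cases in the oral azacitidine-treated subjects occurred during the first 56 days on treatment". That is not supported either. Section 1.4.1 describes those deaths in subjects randomized to the 21-day schedule, and nothing ties them to this text. Within 56 days (two 28-day cycles) the recovery rule can bear only on the start of Cycle 2.

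**Conclusion.** The inconsistency is real but narrow. It concerns a subject whose ANC fell to Grade 4 (or by 50% within it) with no dose held, and who is still Grade 4 and unrecovered when the next cycle is due. For that subject 8.2.4 and Table 2, read alone, point to a capped number of dosing days, and 8.2.5 points to delay. Separately, the recovery formula does not say which cycle's Day 1 it uses, and as printed it is met by any value at or above nadir.

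For one subject, the difference is between starting on the due date and waiting for recovery. The documents do not say how many subjects this affects. By the January 2019 cut-off all 216 analyzed subjects had completed 12 months or discontinued treatment, so the Cycle 1 and 2 case is past for them. What remains open is the Extension Phase, where Appendix J requires as a minimum only one blood count before each cycle, so a Grade 4 value may first be seen when the next cycle is due.

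Confidence is moderate. The conclusion assumes that Figure 2 does not already state the order of the rules. If it does, the text of 8.2.4 and Table 2 should still be made to match it.

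**What to change.** Reconcile Section 8.2.4, Table 2, Section 8.2.5 (including its closing bullet) and Figure 2 so that they:

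1. state one trigger for the recovery requirement that works whether or not a dose was held;
2. describe the same population for the Day 1 Grade 4 rule in the 8.2.4 text and in Table 2;
3. state the order in which the start rule in 8.2.5 and the cap in 8.2.4 apply;
4. identify which cycle's Day 1 stands on the right of the recovery formula.

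Appendix J should then point to the reconciled text. Which rule is clinically right is for the sponsor and the investigators, and no view is taken here. The cost is wording in an amendment or clarification letter, with no new assessments.

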6. SUBJECT DISPOSITION

All subjects screened/randomized will be included in these analyses.

The disposition of subjects will be summarized with counts and percentages. Summaries will include the number of subjects screened and randomized. For subjects randomized, subject disposition will be summarized for analysis population by treatment group and overall for:

- ITT Population
- mITT Population
- Safety Population

Reasons for excluding subjects from mITT population will be summarized and listed for each subject in the ITT population. A separate listing will be provided for subjects who were not randomized. A frequency table of enrollment by site and treatment will be provided.

The reasons for excluding subjects from mITT population are:

1. Did not have at least one post-baseline efficacy assessment;
2. Did not meet all inclusion/exclusion criteria;
3. Did not receive a minimum of one cycle of treatment.

The post-baseline efficacy assessments include any type of transfusions, local or central lab of Hgb and/or platelets count, disease status assessment (by investigator), IWG MDS Response assessment (by investigator), and assessment of bleeding events.

Subjects who have been dosed in Cycle 2 will be considered as receiving a minimum of one cycle of treatment. For subjects who did not have Cycle 2 treatment, they will be considered as receiving a minimum of one cycle of treatment if: 1) they have been dosed (actual dose) for at least 21 days if they were assigned to “21 days” dose; or 2) they have been dosed (actual dose) for at least 14 days if they were assigned to “14 days” dose. Days with missing (or zero) dose due to any reason will not be included in the “21 days” or “14 days”.

Number of subjects who are ongoing in treatment and number of subjects who are ongoing in follow-up will be tabulated. Reasons for study drug discontinuation as collected on the CRF will be summarized for all ITT subjects with the following categories:

- Adverse events
- Lack of efficacy
- Withdrew consent
- Death
- Lost to follow-up
- Protocol violation
- Progressive disease
- Sponsor Decision
- Other

Reasons for study discontinuation as collected on the CRF will be summarized for all randomized subjects with the following categories:

- Death
- Adverse Event
- Pregnancy
- Progressive Disease
- Lack of Efficacy
- Recovery
- Withdrew Consent
- Non-compliance with study drug
- Lost to follow-up
- Study terminated by sponsor

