group. Median follow-up time by treatment will be estimated using KM methods. The analysis of the OS endpoint will be repeated for the mITT population as a supportive analysis.

To assess the potentially confounding effects of other cancer therapy received subsequent to the protocol therapy on the survival estimates, a sensitivity analysis based on the ITT population, will be performed using modified censored criteria. For this analysis, subjects who received subsequent therapy for MDS following discontinuation from their protocol therapy will be censored on the date that the subsequent therapy was started regardless of their survival status at the time of the final analysis. This modified time-to-death endpoint will be analyzed using the same methods as described above for the key secondary efficacy analysis.

The supportive and sensitivity analyses for the OS endpoint will be performed only at the time of the final analysis of OS.

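### SAP 9.1 and 9.8 measure 14-day cycles by the 21-day schedule, so the relative dose intensity of fully adherent 14-day subjects is misreported

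*Protocol*

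**What the plan says.** Protocol 8.2.4 states: "All subjects in Cycle 1 or 2 will receive CC-486 for 14 days of a 28-day cycle schedule". Its step table for this schedule makes 300 mg for 14 days the base level and 300 mg for 21 days one step above it. A move to 21 days after Cycle 2 depends on tolerability, on no sign of hematological improvement, and on agreement with the Medical Monitor. The neutropenia rules in 8.2.4 and Table 2 are written for the same schedule: with Grade 4 ANC on Day 1, dosing in that cycle is limited to "a maximum of 7 days when already on a 14-day dosing schedule". Protocol Section 6 gives the drug holiday as 7 days for 21-day schedules, and as 14 and 21 days for 200 mg on 14-day and 7-day schedules.

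The SAP recognises 14-day assignment. Section 6 has a separate branch for it, and 9.9 counts subjects assigned 300 mg x 14 days in Cycle 1 or 2. The exposure definitions do not follow. SAP 9.1 sets the end of treatment duration at 7 days after the last dose (or death, if earlier) and describes those 7 days as each cycle's rest period. SAP 9.8 divides cumulative dose by that duration, then by a planned intensity of 225 mg/day for every subject. It reports RDI in four bands: below 75%, 75 to 85%, 85 to 100%, and above 100%.

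**The concern.** RDI is read as the share of planned treatment that was delivered. For a subject planned at 14 days, the planned intensity is too high by half (225 against 150 mg/day), while the rest period after the last cycle is 7 days too short. The two errors pull in opposite directions, and the second weakens as cycles accumulate. Reported RDI therefore drifts with time on treatment although adherence is constant.

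At stake is the exposure table. Subjects who took every planned dose would appear under-dosed, some in the lowest band, and the band would depend on how long they stayed on treatment. SAP 9.4 inherits the duration error, because average cycle length is treatment duration divided by number of cycles.

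**Working it through.** **Inputs.** Dose 300 mg; 14 or 21 dosing days in a 28-day cycle (protocol 8.2.4); 7 days added after the last dose (SAP 9.1); planned intensity 225 mg/day (SAP 9.8). The 14-day rest for 300 mg x 14 days is 28 - 14, and matches the holiday that protocol Section 6 gives for 200 mg x 14 days. Every dose is assumed taken, with no cycle delays.

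**The SAP's own figure.** 300 x 21/28 = 225 mg/day, reproduced. For 14 days the plan is 300 x 14/28 = 150 mg/day.

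**Formula.** RDI = cumulative dose / (days from first to last dose, inclusive, + 7) / 225.

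| Schedule, fully taken | Dose (mg) | Duration (days) | mg/day | RDI under the SAP |
|---|---|---|---|---|
| 1 x 14 days | 4,200 | 14 + 7 = 21 | 200.0 | 88.9% |
| 2 x 14 days | 8,400 | 28 + 14 + 7 = 49 | 171.4 | 76.2% |
| 3 x 14 days | 12,600 | 56 + 14 + 7 = 77 | 163.6 | 72.7% |
| 6 x 14 days | 25,200 | 140 + 14 + 7 = 161 | 156.5 | 69.6% |
| 2 x 14, then 1 x 21 | 14,700 | 56 + 21 + 7 = 84 | 175.0 | 77.8% |
| 2 x 14, then 4 x 21 | 33,600 | 140 + 21 + 7 = 168 | 200.0 | 88.9% |

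A subject on 21 days throughout scores 100% at any number of cycles. Average cycle length under SAP 9.4 is 21 days after one 14-day cycle and 49/2 = 24.5 after two, although each cycle lasts 28.

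**Changing one definition only.**
- Rest period only: 4,200/28/225 = 66.7%, and the same for two or six cycles. This is stable, but it is still a share of the 21-day regimen.
- Denominator only: 4,200/21/150 = 133.3% after one cycle, 8,400/49/150 = 114.3% after two. This overshoots.

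**Changing both.** 4,200/28/150 = 100%; 8,400/56/150 = 100%. For 2 x 14 then 4 x 21, planned intensity is (2 x 150 + 4 x 225)/6 = 200, and 33,600/168/200 = 100%.

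**Two checks on the change.**
- A 21-day subject who stops after 10 doses scores 3,000/17/225 = 78.4% before and after, because the 7-day rest still applies. Ending duration at Day 28 of the last cycle instead would move that subject to 3,000/28/225 = 47.6%.
- A 14-day subject capped at 7 doses in a single cycle scores 2,100/14/225 = 66.7% now. If the cap leaves the assigned schedule at 14 days, the result is 2,100/21/150 = 66.7%. The toxicity reduction stays visible.

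**The case against.** The best defence is that 225 mg/day is a deliberate common yardstick. SAP 4.1.2 describes randomization to 300 mg for 21 days, and SAP 9.8 applies its denominator to everyone. Adherence is measured elsewhere: SAP 9.10 uses the intended dose, 9.5 reports days dosed per cycle, and 9.9 counts 14-day subjects. That defence covers the denominator, and showing a 225-based figure is reasonable. It does not cover the rest period. Against a common yardstick, a fully adherent 14-day subject should score 66.7% at any number of cycles, and SAP 9.1 gives 88.9% falling towards that value.

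The affected group may also be small or empty. SAP 8.2 gives baseline transfusion rules only for subjects randomized under the original protocol and Amendments 1 and 2. SAP 6 and 9.9 do provide for 14-day assignment, so the question stays open. This limits the size of the problem without making the definitions right.

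A reader might infer something stronger: that the mITT wrongly excludes subjects who obeyed the Grade 4 cap. SAP 6 says "Subjects who have been dosed in Cycle 2 will be considered as receiving a minimum of one cycle of treatment". Without Cycle 2 dosing, a 14-day subject qualifies only if "they have been dosed (actual dose) for at least 14 days if they were assigned to" that schedule, and "Days with missing (or zero) dose due to any reason will not be included in the" count. Seven permitted doses therefore fall short of 14. The reading is literal and correct, but the documents do not make it an error. The rule is an explicit threshold in days actually dosed. The protocol nowhere says that capped dosing counts as a full cycle, and no affected subject is shown. The population is supportive only: "The analysis of the OS endpoint will be repeated for the mITT population as a supportive analysis". Counting all permitted doses as one cycle would also remove any minimum exposure, since a subject held after three doses could qualify.

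**Conclusion.** SAP 9.1 and 9.8 are wrong as written for 14-day cycles. The issue is minor and limited to exposure summaries. For a fully adherent subject kept on 14 days, RDI falls short of 100% by 11.1, 23.8, 27.3 and 30.4 percentage points after 1, 2, 3 and 6 cycles, which spreads identical adherence over three of the four bands. Only subjects kept on 14 days for three or more cycles fall below 75%. Those who move to 21 days at Cycle 3 score 77.8% after three cycles and 88.9% after six.

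These figures assume 28-day cycles without delay and every dose taken. How many subjects they describe is not stated. The ITT and mITT efficacy analyses, SAP 9.10 compliance and the alpha-controlled tests do not use these definitions. The mITT threshold in SAP 6 is a design choice with no shown effect, and no change to it is proposed.

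**What to change.** Make both edits together.

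- **SAP 9.1:** end treatment duration at the last dose plus the rest period of the schedule assigned in the last cycle (7, 14 or 21 days for 21-, 14- or 7-day schedules), or at death if earlier. State that a Grade 4 neutropenia cap does not change the assigned schedule; Table 2 makes a schedule reduction a separate step, after two consecutive cycles of Grade 4.
- **SAP 9.8:** use 150 mg/day for cycles in which 300 mg x 14 days was the protocol-planned schedule and 225 mg/day otherwise, averaged over a subject's cycles. After a toxicity reduction, keep the plan in force before it as the denominator, so that true reductions still lower RDI.
- **Reporting:** show the 225-based RDI alongside. The SAP was signed in March 2019 and the primary study report is final, so the revised figure is post hoc and should be labelled as such. Give the number of 14-day subjects by arm, which SAP 9.9 already produces; if it is zero, one sentence closes the matter.

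The cost is two derivation edits and one rerun of the exposure tables, using dosing data already collected. Treatment duration and average cycle length will also shift for subjects whose last cycle was on a 14- or 7-day schedule. Subjects whose last cycle was on 21 days keep their current duration.
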